5.5. Variables

5.5.1. Primary outcome

✓ Proportion with low birth weight (<2500gm)

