LAMPREG study

Statistical Analysis Plan (SAP) statement

Version 1.0 – February 2021

Section 1: Administrative information

1. Title and Trial registration

Statistical analysis plan for the LAMP for Malaria in Pregnancy (LAMPREG) trial: "Active case detection and treatment of malaria in pregnancy using LAMP technology: A pragmatic randomized multi-Center diagnostic outcomes trial"

This trial is registered in clinicaltrial.gov: registration number NCT03754322

2. SAP version

Version: 1.0, Date: February 22nd, 2021

3. Protocol version

This document has been written based on information contained in the study protocol version 1.5, dated February 22^{nd} , 2021.

4. SAP revisions – revision history

Protocol version	Updated	SAP	Section	number	Description of and	Date changed
	version no.		changed		reason for change	
1.5	1.0		First SAP	version		February 22 nd , 2021

5. Roles and Responsibility – non signatory names and contribution

This SAP protocol was written and designed by

- [name], Post-Doctoral Associate, [name] Lab, The University of Calgary, AB, Canada
- [name], MD, AHRI, Addis Ababa, Ethiopia

• [name], MD, MSc, alumni [name] Lab, The University of Calgary, AB, Canada (current position, Microbiology Fellow, NIH, UK)

6. Roles and Responsibility – signatures

• [name], MD, PhD, PI of the LAMPREG study

Name	Name
Signature:	Signature:
Date:	Date:

Section 2: Introduction

1. Background and rationale

Malaria is an infectious disease transmitted by *Anopheles* mosquito. Pregnant women are particularly susceptible to adverse outcomes in terms of maternal and fetal health. Several prevention strategies are available to public health authorities to prevent malaria. These strategies are anti vectorial (bed nets, monitoring of stagnant water where mosquito larva bread), intermittent preventive treatment or repetitive screening during antenatal care (ANC). All the above mention strategy present limitations that impair their efficiency to prevent malaria-associated morbidity.

The LAMPREG trial aims to fill the knowledge gap by proposing an alternative systematic screening strategy using point of care (POC) compatible molecular biology techniques.

2. Objectives

Research hypothesis: The trial hypothesis is that enhanced LAMP-based malaria detection during ANC will lower the proportion of malaria-associated adverse outcomes (low birth weight, pregnancy loss, anemia). The proportion of Low Birth weight is the study primary outcome.

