The laboratory testing post trial (gold standard testing, parasitic variant assessment) is scheduled for 2 years post sample collection, with analysis and publication of results within a 3-year frame (end of 2022- first semester of 2023).

7. Timing of outcome assessments

The scheduled of ANC visit is given in the study protocol (v1.5 – see table 5).

Section 4: Statistical Principles

1. Confidence intervals and p-values

All applicable statistical tests will be two-sided and will be performed using a 5% significance level.

All confidence intervals presented will be 95% and two-sided.

2. Adherence and Protocol Deviations

Protocol adherence is defined by the completion of all ANC visit as per study arm (included treatment course completion for women eligible) and the follow-up of the newborn for 28 days post-delivery.

Nonadherence is defined by the number of missed visits, the loss to follow-up or the absence of recorded birth weight.

Protocol deviation is defined as:

- Non-administration of malaria treatment for LAMP positive women in the intervention arm
- Incomplete treatment administration for any treated women
- Loss to follow up or partial course of ANC visit

3. Analysis population

The intention-to-treat population will include all randomized patients, according to the study arm they were randomized in.

Section 5: Trial population

1. Screening data

The following summaries will be presented for all screened patients: inclusion time frame, number of the screened expecting mothers, number of mothers recruited per month, the reason for non-recruitment. This summary will be presented overall and by study center.

2. Eligibility

Eligibility criteria are presented in the study protocol v1.5.

To summarize, all pregnant women >18 years old, with gestational age < 27 weeks and attending ANC care in any of the study centers is eligible to the study

3. Recruitment

The "CONSORT" diagram comprising the number of people screened, eligible, consented, randomized, receiving their allocated intervention (malaria diagnostic and treatment) and followed to delivery will be presented with the study results.

4. Withdrawal/Follow-up - level of withdrawal

The level of consent withdrawal will be tabulated (classified as "consent to continue follow-up, sample and data collection" "consent to continue follow up and data collection", "complete –no further follow-up or

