data collection", "lost to follow up". This will be presented in CONSORT diagram format rather than as a table, with numbers and reasons for withdrawal and/or exclusion from the analysis given at each stage. The numbers (with reasons) of losses to follow-up (dropouts and withdrawals) over the course of the trial will be summarized by treatment arm.

5. Population and subgroup to be analyzed

Intention-to-treat (ITT): All randomized study subjects. This will be the primary population for the analysis.

Per Protocol (PP): All randomized study subjects completing the whole study period (complete cases). For a specific analysis, study subjects with missing data on any of the variables in the model will be excluded from the analysis. Analyses of this population is seen as a sensitivity analysis to investigate whether conclusions are sensitive to assumptions regarding the pattern of missing data

We will analyze independently the following subgroups (Both ITT and PP populations):

- a. Primiparous mother
- b. **Asymptomatic malaria**: women who did not present symptom at any ANC visit but were detected positive for *Plasmodium* spp infection by any diagnostic method.
- c. **Sub microscopic malaria**: any women diagnosed positive for malaria by molecular method (LAMP or post hoc gold standard RT-qPCR)
- d. Malaria species identified: *P. falciparum*, *P. vivax* and mixed infections (3 subgroups)
- e. Women presenting positive malaria testing in placental blood at delivery
- f. Women from newborn with Low Birth Weight

6. Baseline patient characteristics

Expectant women will be described with respect to age, parity, gestity, gestational age, history of malaria, pregnancy complication, both overall and separately for the two randomized groups. These data will be summarized in a table.

Section 6: Analysis

1. Outcome definition

Primary study outcomes are related to newborn health: fetal anemia (hemoglobin <12.5 g/dL), mean birthweight, low birthweight (<2500 g), mean gestational age, preterm delivery (<37 weeks' gestation), mean birthweight for gestational age (Z scores), small for gestational age, fetal loss (spontaneous abortion at <28 weeks' gestation or stillbirth), and the composite outcomes of adverse livebirth (preterm, low

birthweight, or small for gestational age) and adverse pregnancy (adverse livebirth or fetal loss). Mortality outcomes included neonatal, perinatal, and mortality up to age 4 weeks.

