Secondary outcomes were signs of placental malaria infection at delivery, defined as a composite of maternal malaria (detection of infection in peripheral blood with post hoc gold standard testing) or placental malaria (detection of infection in placental blood with microscopy, molecular testing for active infection, or malaria pigment in blood smear monocytes for signs of past infection)

Secondary outcomes include maternal anemia (any: hemoglobin level <11 g/dL; moderate: hemoglobin level <9 g/dL) during each ANC visit and at delivery. We will use the categories "no anemia", "mild anemia", "moderate anemia" and "severe anemia" using the reference values for each pregnancy trimester. Values will be disaggregated according to gestational age.

Secondary outcomes during pregnancy comprised maternal malaria, detected with any method and by each method separately. This outcome was further stratified by patent infection (positive microscopy or malaria rapid diagnostic test) and sub-patent infection (negative microscopy and malaria rapid diagnostic test and positive LAMP–PCR). Morbidity outcomes assessed during pregnancy comprised clinical malaria (documented or history of fever plus positive malaria rapid diagnostic test or microscopy) and unscheduled clinic visits for any reason and for all reasons unrelated to malaria.

2. Analysis methods

Mean values of quantitative variables will be compared using a two-sided t-test with a significance of p < 0.05. We will use a negative binomial model to assess the effect of asymptomatic malaria screening using the number of (i) both microscopic and submicroscopic and (ii) submicroscopic *P. falciparum* infections occurring during pregnancy with an adjustment for the confounding variables. Multiple test correction will be implemented.

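### SAP 5.5 subgroups e and f are defined by trial outcomes: LBW carries no information inside f, and no arm comparison inside e or f is protected by randomisation

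*SAP*

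**What the plan says.** SAP Section 5.5 introduces its subgroup list with "We will analyze independently the following subgroups (Both ITT and PP populations". Item e is "Women presenting positive malaria testing in placental blood at delivery" and item f is "Women from newborn with Low Birth Weight".

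Both items are also outcomes of the trial:

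- **Item f.** SAP Section 2.2 states: "The proportion of Low Birth weight is the study primary outcome". Protocol 5.5.1 names the same outcome, with a threshold of 2500 g.
- **Item e.** SAP Section 6.1 states: "Secondary outcomes were signs of placental malaria infection at delivery, defined as a composite of maternal malaria" or placental malaria, the latter including infection found in placental blood. Secondary objective b in SAP Section 2.2 makes placental malaria one of the measures by which the intervention's impact is judged.

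On the population, SAP Section 4.3 states: "The intention-to-treat population will include all randomized patients, according to the study arm they were randomized in". SAP Section 3.4 sets a superiority aim for the intervention arm. SAP 5.5 gives no purpose for e or f, does not restrict them to description, and offers no method for selection after randomisation. Nor does it say in words that the arms will be compared inside them.

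**The concern.** Membership of e or f is known only at delivery, and the trial's own hypothesis is that the intervention changes who belongs. Randomisation makes the arms comparable among all women randomised. It does not make them comparable among women picked out by an event that happens later and that treatment may influence.

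In f there is a further fault: every newborn has the primary outcome by definition. At stake is the reporting of a pre-specified subgroup result, such as prematurity or neonatal death among LBW births, as an effect of screening when part or all of it comes from the selection. The multiple-testing correction promised in SAP Section 6.2 does not address this, because the problem is who is compared and not how many tests are run.

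**Working it through.** **Design rates.** SAP Section 3.3 and Protocol 5.6 give LBW of 17.3% (standard of care, SOC) and 12.3% (LAMP), two-sided alpha 0.05 (SAP Section 4.1), 80% power, 3:1 allocation, continuity correction and 20% attrition. The pooled-variance formula with continuity correction gives 538 SOC women, so 538 × 4 = 2152 in all; 2152 × 1.2 = 2582.4, which rounds up to the stated 2583. These rates are used below.

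**Size of f.** After 20% loss, 2583 × 0.8 ≈ 2066 women remain.

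- At 3:1: 516.6 × 0.173 ≈ 89 SOC and 1549.8 × 0.123 ≈ 191 LAMP LBW births.
- At the 1/3 v 2/3 split in SAP Section 3.2: 688.8 × 0.173 ≈ 119 and 1377.6 × 0.123 ≈ 169.

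**LBW inside f.** It is 100% v 100%: risk ratio 1 and difference 0, whatever the true effect. The same holds when f is split by malaria status. The SAP 6.1 adverse-livebirth composite, which includes LBW, is likewise 100% among live births in f.

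**Other events inside f.** Let x be the percentage of all births that are LBW and have the event. Then

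ratio inside f = (x_LAMP / 12.3) ÷ (x_SOC / 17.3) = (x_LAMP / x_SOC) × 17.3/12.3 = true ratio × 1.41.

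**Preterm LBW.** Assume 40% of the LBW babies that remain under LAMP are preterm (not in the documents): x_LAMP = 0.40 × 12.3 = 4.92. Vary the preterm share of the 5 points prevented:

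| Preterm share of prevented LBW | x_SOC | True ratio | SOC inside f | LAMP inside f | Ratio inside f |
|---|---|---|---|---|---|
| 0% | 4.92 | 1.00 | 28.4% | 40.0% | 1.41 |
| 40% | 4.92 + 2.0 = 6.92 | 0.71 | 40.0% | 40.0% | 1.00 |
| 60% | 4.92 + 3.0 = 7.92 | 0.62 | 45.8% | 40.0% | 0.87 |

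**Neonatal death inside f (assumed risks).**

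- Prevented LBW carries 5% mortality and remaining LBW 10%: SOC (5 × 0.05 + 12.3 × 0.10)/17.3 = 8.6%, LAMP 10.0%, ratio 1.17. Yet deaths from LBW births fall from 1.48% to 1.23% of all births.
- Risks reversed: SOC (5 × 0.10 + 12.3 × 0.05)/17.3 = 6.4%, LAMP 5.0%, ratio 0.78.

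**Mean birth weight inside f.** Assume normal weights with SD 400 to 600 g (not in the documents). The shift that moves LBW from 17.3% to 12.3% is 87 to 131 g overall. The means below 2500 g, μ − SD·φ(a)/Φ(a) with a = (2500 − μ)/SD, differ by only 17 to 25 g, about 19% of the true shift.

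**Subgroup e (assumed values).** Let 40% of women be at higher risk, with outcome risk 20% v 10% in the rest, and no effect of arm on the outcome. Placental positivity under SOC is 10% (lower risk) and 30% (higher risk). The higher-risk share of e under SOC is 0.4 × 0.30 / (0.6 × 0.10 + 0.4 × 0.30) = 0.12/0.18 = 66.7%, so outcome risk inside e is 16.7%. Under LAMP:

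- Positivity 3% and 24%: share 0.096/0.114 = 84.2%, risk 18.4% (false harm).
- The same proportional reductions swapped, giving 8% and 9%: share 0.036/0.084 = 42.9%, risk 14.3% (false benefit).
- Positivity halved in both, 5% and 15%: share 66.7%, risk 16.7% (no bias).

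**The case against.** The strongest reply is that the SAP never states an arm comparison inside e or f. Protocol 5.8 describes subgroup analysis as serving potential confounders and the comparison of LAMP with microscopy positivity in the intervention arm. SAP Section 6.2 plans relative risks by malaria status. A description of infection among mothers of LBW babies, or among placenta-positive women, would be legitimate.

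This stands in part: arm comparison is inferred. But the list is to be run in an ITT population defined by randomised arm, under a superiority aim, with no limit to description. The malaria-status reading does not rescue LBW in f, which is constant there too.

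A reader might also infer stronger points that the documents do not support:

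- **That LBW is uninformative in e as well.** It is not; LBW still varies among placenta-positive women. That comparison is exposed to selection but is not empty.
- **That f must show the intervention as harmful.** The direction cannot be derived. The ratios above fall on both sides of 1, and in e the bias can be zero.
- **That 1.41 is the expected false signal for preterm birth.** It is the ratio seen only if every prevented LBW baby is term. Protocol 1.2 and 5.3.1 link malaria in pregnancy to prematurity, so some prevented babies could be preterm. The multiplier also depends on the effect: Protocol 1.2 attributes about 19% of LBW in endemic areas to malaria, against 5/17.3 = 29% removed at the design rates. Removing 19% gives 1/0.81 = 1.23.
- **That the main result is at risk.** The primary LBW comparison uses all randomised women and does not pass through these subgroups.

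**Conclusion.** The point holds in a limited form. Inside f the primary endpoint is fixed at 100% by definition, which needs no assumption. Every other arm comparison in f, and every arm comparison in e, lacks the protection of randomisation. At the design rates, f multiplies the per-birth ratio of any event among LBW births by 1.41, so a neutral effect can look harmful and a real benefit can disappear or shrink. That multiplier rests on the planned 17.3% and 12.3%. The preterm, mortality, birth-weight and placental examples rest on assumed values and show what can happen, not what will. That arms will be compared inside e and f is the natural reading of the SAP and not its stated text. The consequence is confined to subgroup reporting; it is worth correcting before analysis because these results would otherwise count as pre-specified.

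**What to change.** In SAP 5.5, remove e and f from the subgroups used for arm comparison, and state that no arm-effect estimate or p-value will be reported within them. Keep placental infection as the secondary outcome it already is in SAP 6.1, compared by arm in all randomised women. Present mothers of LBW babies and placenta-positive women in descriptive tables only, and say so.

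The cost is SAP wording and the loss of two subgroup contrasts that could not support a conclusion about the arms. No new data are needed. Adding subgroups based on features fixed at randomisation is optional and not needed to cure this fault. Subgroups b, c and d also depend on findings after randomisation; this change does not settle how they should be used.

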symptomatic and asymptomatic first and second trimester mothers will be included in the study and individually randomized to one of two arms: standard of care or enhanced cased detection arms using LAMP for malaria. Mothers will be enrolled during a twelve-months period from October 2020 to October 2021 and then followed until 28 days after delivery. Given the rate of pregnant mothers at the locations, we anticipate that the required minimum of 2583 mothers will be enrolled in the study during the study period. In the first standard of care arm, venous blood sample will be collected from each study participant and the presence of *Plasmodium* infection will be diagnosed by microscopy in symptomatic patients. Pregnant women who test positive for malaria will be referred and treated for malaria with quinine or ACTs as per national guidelines. In the second (test) arm, mothers whether symptomatic or asymptomatic will be tested by a commercially available CE-approved LAMP malaria test (Meridien Biosciences, Illumigene Malaria M kit, Cincinatti, USA) and Human Diagnostics LoopAMP (Wiesbaden, Germany) at each clinic visit in addition to RDT/microscopy. The commercial LAMP tests can distinguish P. falciparum and P. vivax and treatment will be given according to national guidelines. The purpose of doing all tests in the intervention arm is to determine how many additional cases LAMP identified. The primary outcome is the proportion of deliveries with low birth weight, with secondary outcomes of: (i) absolute birth weight; (ii) maternal hemoglobin; (ii) neonatal hemoglobin at birth (Standard Hgb testing from peripheral blood or finger prick); (iv) neonatal mortality; (v) stillbirth; and (vi) prematurity in each of the two arms. Additionally, signs of current or past *Plasmodium* sequestration in the placenta will be evaluated.

[figure not shown]

Figure 1: Flowchart summarizing randomized trial

There will be a total of at least five antenatal visits (mandatory). Emergencies (medical consultation outside the planned visit) will be recorded for each included woman. Visit 1 and 2 may be combined for mothers who present in the second trimester. The following table summarizes the procedures to be conducted at each visit.

Visit #	Time frame	Aim	Action for the study
1	Visit at health care center	Inclusion	Enrolment and randomisation
2	26 weeks gestation	Follow up	Malaria testing as per inclusion arm (2mL venous blood on EDTA) +ANC regular care Maternal Hgb

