5.5.3 Other endpoints

Performance of LAMP, RDT, Microscopy, compared to qRT-PCR (gold standard) including sensitivity, specificity, PPV, NPV. Signs of *Plasmodium* infection: current (with presence of asexual parasites in placental blood), or past infection (presence of malaria pigment).

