5.7.3. Malaria microscopy and RDT

Blood film will be air-dried at room temperature and the thin blood film will be fixed with absolute methanol. Then, blood film will be stained with 10% Giemsa solution for 10 minutes and examined by experienced laboratory technician. The presence of *Plasmodium* will be ruled out if no parasites are observed after examination at least 100 microscopic fields with hundred (100x) objective. Parasitemia will be estimated in thick film by counting the number of asexual parasites along with 200 white blood cells (WBC) or 500 WBC if the parasite count is less than 10 parasites per 200 WBC. A total of 8,000/µl white blood cells count will be considered for the determination of parasitemia. At delivery, placental blood will be collected with anticoagulant and immediately dried as a smear on a microscope slide. Placental blood smear will be air dried then stained using

10% Giemsa (as for regular peripheric blood samples). Presence of asexual parasites or malaria pigment will be recorded.

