Primary objective:

The primary objective of this trial is to evaluate the effectiveness of LAMP-based enhanced malaria detection in improving pregnancy outcomes as measured by birth weight, neonatal anemia, maternal anemia, and stillbirth.

Secondary objective:

The secondary objectives are:

- a. To determine the proportion of asymptomatic MiP cases revealed by microscopy, RDT and LAMP
- b. To evaluate the impact of the intervention in terms of malaria-associated placental damage as evaluated by placenta weight and placental malaria.
- c. To evaluate the performances of IllucidX LAMP(ultrasensitive) compared to the approved method using the samples from the trial.
- d. To compare the diagnostic performance of microscopy, RDT and LAMP against qRT-PCR in MiP.
- e. To decipher parasitic genotypes that may impair diagnostic test performances and treatment efficacy using parasite whole-genome sequencing.

Section 3: Trial Methods

1. Trial design

The study is a prospective diagnostic study of malaria in pregnant women. The goal is to determine whether: (i) LAMP provides a clinically measurable benefit compared to current first-line diagnostic test of Giemsastained microscopy and whether (ii) enhanced case detection of asymptomatic mothers with LAMP has added value in terms of outcomes. We hypothesize that addition of LAMP to one arm will be of greater benefit than microscopy alone due to additional LAMP sensitivity. We further hypothesize that enhanced case detection by screening asymptomatic mothers at each antenatal visit will be of additional value in treating malaria. Both symptomatic and asymptomatic first and second trimester mothers will be included in the study and individually randomized to one of two arms: standard of care or enhanced cased detection arms using LAMP for malaria. Mothers will be enrolled during a twelve-months period from March 2021 to July 2022 then followed until 28 days after delivery

2. Randomization

Women will be screened for eligibility and randomized either in the Standard of Care (SOC, 1/3 of included women) arm or in the intervention arm (2/3 of included women).

Randomization will be implemented at each health center. Stratification per parity (primiparus, second pregnancy and \geq 3 pregnancy) will be implemented to avoid confounding factor of acquired immunity for MiP variants.

3. Sample size

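### The SAP's placental malaria outcome can be met by peripheral-blood infection alone, so a difference between arms cannot be attributed to the placenta

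*SAP*

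**What the plan says.** SAP Section 6.1 (Outcome definition) gives as a secondary outcome "signs of placental malaria infection at delivery, defined as a composite of maternal malaria" or placental malaria. It defines the two components in brackets:

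- Maternal malaria: "detection of infection in peripheral blood with post hoc gold standard testing".
- Placental component: "detection of infection in placental blood with microscopy, molecular testing for active infection, or malaria pigment in blood smear monocytes for signs of past infection".

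SAP Section 2.2, secondary objective (b), concerns "malaria-associated placental damage as evaluated by placenta weight and placental malaria". SAP Section 5.5, subgroup (e), is "Women presenting positive malaria testing in placental blood at delivery".

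Protocol v1.1 treats the endpoint as placental throughout. Section 5.2 says that signs of current or past "sequestration in the placenta will be evaluated". Section 5.5.3 defines infection as "current (with presence of asexual parasites in placental blood), or past infection (presence of malaria pigment". Section 5.7.3 describes a Giemsa-stained smear of placental blood: "Presence of asexual parasites or malaria pigment will be recorded".

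**The concern.** The components are joined by *or*, so either is enough. A woman with a positive peripheral test, a negative placental smear, a negative placental molecular test and no pigment is analysed as having signs of placental infection.

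Objective (b) asks whether the intervention protects the placenta. If the composite falls in the LAMP arm, the reader cannot tell whether placental infection fell or whether fewer women carried parasites in peripheral blood at delivery. If it does not fall, a real placental effect may have been obscured. As the SAP stands, either the composite or its placental part could be presented as the placental result after the data are seen.

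**Working it through.** **Comparison of the definitions.** The documents give no rate, effect size or power for the placental outcome, so there is no figure of the plan to reproduce.

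| Place | Peripheral blood counts? | Placental blood or pigment counts? |
|---|---|---|
| SAP 6.1, composite | Yes, alone | Yes |
| SAP 6.1, placental malaria component | No | Yes (microscopy, molecular, pigment) |
| SAP 2.2, objective (b) | No (placenta weight and placental malaria) | Yes |
| SAP 5.5, subgroup (e) | No | Yes (placental blood) |
| Protocol v1.1, 5.2, 5.5.3 and 5.7.3 | No | Yes (parasites or pigment) |

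Only the composite admits peripheral infection alone.

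**Does another listed outcome answer objective (b)?** Placenta weight is not among the outcomes in SAP 6.1. Subgroup (e) is defined by a result obtained after randomization, so analysis within it does not estimate the effect on placental malaria. The placental component is defined, but the SAP does not commit to comparing it by arm. The composite is therefore the only listed outcome that serves objective (b).

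**Are the two sites interchangeable?** Protocol 5.3.1 says that the placenta may hold parasites when none are documented peripherally. Protocol 5.12 says that submicroscopic infection raises the risk of placental malaria. That is an association, not an identity, so a positive peripheral test does not establish placental infection.

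**Dilution: an illustration on assumed rates.**

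- From the documents: total 2583, attrition 20%, allocation 3:1 (SAP 3.3), two-sided 5% level (SAP 4.1). Evaluable: 2583 × 0.8 ≈ 2066, about 517 standard of care and 1550 LAMP.
- Assumed: placental malaria in 10% of the standard-of-care arm and a true risk ratio (RR) of 0.70, so 7% in the LAMP arm.
- Let q be the proportion of the standard-of-care arm who are peripheral-only positive, and r the RR for those infections. Composite RR = (0.07 + q·r) / (0.10 + q).
- Power uses the normal approximation for two proportions, with pooled variance under the null and unpooled under the alternative, and no continuity correction.

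| q | RR, r = 1 (no effect on peripheral-only) | Power | RR, r = 0.70 (equal effect) | Power |
|---|---|---|---|---|
| 0 (placenta only) | 0.70 | 59% | 0.70 | 59% |
| 3% | 0.10/0.13 = 0.77 | 48% | 0.091/0.13 = 0.70 | 71% |
| 5% | 0.12/0.15 = 0.80 | 43% | 0.105/0.15 = 0.70 | 77% |
| 10% | 0.17/0.20 = 0.85 | 34% | 0.14/0.20 = 0.70 | 89% |
| 20% | 0.27/0.30 = 0.90 | 26% | 0.21/0.30 = 0.70 | 98% |

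SAP 3.2 describes a one-third to two-thirds split instead of 3:1. At 2:1 the RRs are the same; power is 65% for the placenta-only outcome and 54%, 48%, 39% and 30% down the r = 1 column.

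Dilution thus depends on r. With r = 1 the effect shrinks; with r = 0.70 the RR is unchanged and power rises. In both cases the result is not specific to the placenta.

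**The case against.** **The governing protocol is not available.** The SAP was written from protocol v1.5, and the protocol at hand is v1.1. Objective (b), with its placenta weight, has no counterpart among the v1.1 specific objectives, so v1.5 may have changed the placental endpoints. This stands as a limit: the conflict with the protocol is shown against v1.1 only. The mismatch inside the SAP does not depend on the protocol version.

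**A placenta-only definition already exists in the SAP.** True: the component called placental malaria is the term that objective (b) uses. It would be too strong to say that the SAP has no measure for the objective. What is missing is a stated comparison of that component between arms.

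**Peripheral molecular positivity may be a useful marker of placental infection.** Protocol 5.12 supports an association, so a composite may be worth reporting. That argues for keeping it under an accurate name, not for calling it placental.

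**A reader might infer that peripheral positives would dominate the composite.** The pilot qPCR figure of 11/34 (Protocol section 3) invites this. It comes from one site in peak season, with 26 of 34 women in the first trimester. Table 1 of the same section gives third-trimester PCR positivity of 3/36 (8.3%), in symptomatic women. Neither is a rate at delivery in trial participants.

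**A reader might also infer that dilution is certain.** Suppose placental infection is 10% versus 5% (RR 0.50) and independent peripheral positivity is 20% in both arms. The composite is 1 − 0.90 × 0.80 = 0.28 versus 1 − 0.95 × 0.80 = 0.24, RR 0.86. This assumes independence and no effect on the peripheral infection that the intervention is designed to detect and treat. Halve peripheral positivity in the LAMP arm and the composite there is 1 − 0.95 × 0.90 = 0.145, RR 0.145/0.28 = 0.52, which is almost no dilution. The documents do not say which case applies.

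**Conclusion.** The point holds as a matter of definition. Followed as written, SAP 6.1 counts peripheral-only infection as a sign of placental infection, against objective (b), the SAP's own narrower usage and the protocol v1.1 endpoint. The firm consequence is loss of specificity: an effect on the composite cannot be read as an effect on the placenta.

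Attenuation is possible but conditional. It requires peripheral-only infections to respond less to the intervention than placental ones. The illustrated range, RR 0.77 to 0.90 in place of 0.70, rests wholly on assumed rates and on no effect on peripheral-only infections. The documents do not support a stronger claim that the peripheral part will overwhelm the placental one.

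This is a minor point. The endpoint is secondary in the SAP and listed under other endpoints in the protocol. The primary low birth weight comparison and its sample size are unaffected.

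**What to change.** In SAP 6.1:

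1. Define the objective (b) outcome, compared by randomized arm, as the SAP's existing placental malaria component: parasites in placental blood by microscopy, or by molecular testing where done (active); malaria pigment (past). Report active, past and any.
2. State that the molecular part comes from the SAP. Protocol v1.1 section 5.5.3 has no molecular component, and section 5.7.3 describes only a stained smear of placental blood.
3. Rename the composite *any malaria infection at delivery* and keep it as a separate secondary outcome.
4. Check the wording against protocol v1.5.

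The cost is SAP text and one more secondary comparison, to be covered by the multiple-test correction that SAP 6.2 already promises. Protocol v1.1 already plans placental blood collection, the smear reading and malaria testing at delivery. Only placental molecular testing is not described there, hence the words *where done*.
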